Institutional Review Board Intervention/Interaction Detailed Protocol

Principal Investigator: [name]

Project Title: Fluoxetine treatment of depression in adults with Down syndrome

Version Date: January 31, 2024

1. Background and Significance

Down syndrome (DS) or trisomy 21, is a common genetic syndrome, resulting from an extra copy of chromosome 21. According to the Centers for Disease Control and Prevention, about 6,000 babies are born with DS each year [1] and overall, DS occurs in about 1 in 700 live births [2]. Down syndrome commonly includes characteristic physical features, a variable degree of cognitive impairment, and several medical comorbidities. Medical comorbidities commonly associated with DS include congenital heart defects, thyroid disease, gastrointestinal problems, hematological disorders, hearing loss, ocular disorders, and obstructive sleep apnea [3]. In addition to elevated rates of medical comorbidity, individuals with DS have an increased risk of psychiatric disorders compared to the general population [4–6]. Prevalence rates of psychiatric comorbidities have been reported to be as high as 38% and 35% in children and adults with DS, respectively [4,5]. Externalizing symptoms such as oppositionality, impulsivity, and hyperactivity are more common in children with DS, whereas internalizing symptoms such as depression, anxiety, and social avoidance become more prevalent in adolescence and adulthood [7–9].

Depression is a common comorbidity in adults with DS which is likely underestimated in naturalistic prevalence studies; reported prevalence rates range from 6-18% [9–13]. A recent study which included 605 individuals with DS from England and Wales demonstrated that 12.4% of younger adults (16–35 years) and 18.4% of older adults (≥ 36 years) had a lifetime history of depression based on medical record review [13]. Females and males with DS had a four- and five-fold increased risk of depression respectively, compared to the general United Kingdom adult population [13]. In a separate longitudinal cohort study, 134 adolescents and adults with DS (≥ 16 years) participated in a detailed psychiatric assessment with psychiatrists who had expertise in DS at baseline and two years later [12]. The two-year incidence of a major depressive episode in this study was 5.2% [12]. Adults with DS have several unique risk factors for developing depression compared to the general population including cognitive impairment [14], reduced serotonin brain tissue concentration in post-mortem studies [15], high prevalence of thyroid disorders [3], and significant emotional stressors related to the transition to adulthood and the accompanying loss of school-based programming and services.

Depression is often underrecognized and undertreated in adults with DS. There are several diagnostic challenges related to the inherent communicative and cognitive limitations. While the clinical characteristics of depression in individuals with DS are often similar to those seen in the general population including sad mood, diminished experience of pleasure, decreased appetite and weight loss, social withdrawal, reduced speech, low energy, and psychomotor slowing [6], individuals with DS may have difficulty expressing depressive thoughts such as of guilt, worthlessness, self-deprecation, or thoughts of suicide [10]. These clinical features may necessitate taking into account behavioral observations and caregiver report rather than strict application of diagnostic criteria. A retrospective study assessing the clinical features of depression in DS reported that when strict Diagnostic and Statistical Manual of Mental Disorders, Third Edition (DSM-III-R) criteria were applied, only 50% of depressive episodes diagnosed by expert clinicians met full criteria [10]. This study also demonstrated that depression was frequently misdiagnosed as dementia in individuals with DS and therefore left untreated.

[10]. In a retrospective study of 42 adults with DS, not all patients with depression received pharmacotherapy and no patients received a second medication trial if the first was ineffective [10], suggesting under treatment of a generally treatable psychiatric comorbidity.

Under treatment of depression in DS is, in part, related to the lack of data on effective treatment approaches. A review article on depression in DS published in 2011 highlighted that systematic studies on the treatment of depression were critically needed [16]. Even so, now 10 years later, no additional studies have been published and the literature on pharmacotherapy for depression in DS is limited to small case reports and case series [6]. No systematic, prospective studies on the effectiveness, tolerability, and safety of antidepressants in DS have been conducted. Three case series on pharmacotherapy for depression in DS were published more than 20 years ago, prior to the widespread use of modern antidepressants. These three case series reported on the clinical response to tricyclic antidepressants (TCAs) [17–19] and one of these case series also reported on three patients' response to fluoxetine, a selective serotonin reuptake inhibitor (SSRI) [18]. All three patients who received treatment with fluoxetine had a positive response, two of whom had previously failed to respond to TCAs. Of the remaining six patients described in this case series, three other patients responded to TCAs, one responded to a first generation antipsychotic, and two did not receive pharmacologic treatments. Medication side effects are not reported in any of these case series. The significant medical comorbidities and neurocognitive atypicalities associated with DS limit the extent to which our knowledge of the safety and efficacy of antidepressants in the general population can be extrapolated. Our team has collected preliminary data from 11 patients with DS treated with SSRIs for depression which indicate that patients with DS respond to much lower dosages of SSRIs than the general population and may be more sensitive to behavioral side effects at higher dosages [20]. Because of these issues, DS-specific prospective antidepressant trials are needed to inform clinical best practices.

Selective serotonin reuptake inhibitors are a class of medications which include fluoxetine, paroxetine, sertraline, fluvoxamine, citalopram, and escitalopram. They selectively block the uptake of serotonin and have several Food and Drug Administration (FDA) indications including for the treatment of depression, anxiety disorders, obsessive-compulsive disorder, and posttraumatic stress disorder. Selective serotonin reuptake inhibitors have largely replaced the TCAs as first-line treatment for depressive disorders due to similar efficacy, improved tolerability, and a much safer side effect profile [21]. Unlike TCAs, SSRIs are generally nonlethal in overdose, are not associated with cardiac toxicity, and do not lower the seizure threshold. Modern clinical practice guidelines include SSRIs among the first-line medications for the treatment of depression [22]. Tricyclic antidepressants are considered second-line medications, only to be used after the failure of one or more first-line medications [22]. In clinical practice, SSRIs are typically the first class of medications used to treat depression. A recent study demonstrated that SSRIs comprised 93% of first-line medications for depression in primary care [23]. Selective serotonin reuptake inhibitors have a relatively benign side effect profile and are generally well tolerated. The most common side effects include impaired sexual functioning, sleepiness, and weight gain; 25% of patients consider side effects to be either "very bothersome" or "extremely bothersome" [24]. Despite the widespread use of SSRIs in the general population, their use in patients with DS has only been reported in three patients in a single case series which did not include data on adverse effects or safety [18].

Depression is a common psychiatric comorbidity with a lifetime prevalence of 16.6% in the United States [25]. Adults with DS have a four- to five-times increased risk of developing depression compared to the general population [13], suggesting that up to 70% of individuals with DS may experience depression in their lifetime. Compared to other known comorbidities associated with DS such as obstructive sleep apnea, congenital heart defects, blood cancers, and cataracts, depression is both relatively more highly prevalent and understudied. No reports on the use of modern antidepressants in DS have been published in the past more than 25 years. Our knowledge of the safety and efficacy of antidepressants in the general population may not be applicable to patients with DS because of the associated medical comorbidities and neurocognitive differences.

The central hypothesis of this project is that adults with major depression and DS will experience an improvement in depressive symptoms after a course of fluoxetine treatment. We also expect that fluoxetine will be safe and well tolerated. This study will provide much needed preliminary prospective

data regarding the effectiveness and tolerability of fluoxetine for these symptoms in DS and is a necessary first step prior to conducting a larger, more definitive placebo-controlled trial.

2. Specific Aims and Objectives

Specific Aim 1: Determine whether a 16-week prospective, open-label trial of fluoxetine shows preliminary evidence of effectiveness, safety, and tolerability in adults with DS and major depressive disorder (MDD).

This aim addresses our central hypothesis that fluoxetine will be effective and safe in the treatment of depression in adults with DS.

- A)** For preliminary evidence of effectiveness, we will require an observed response rate (where response is defined as a 16-week CGI-I rating of “much improved” or “very much improved”) of 35% or greater. We will use the CGI-I rather than a depression scale for our effectiveness criterion because of the absence of existing data supporting the usefulness of common scales for quantifying depression severity in adults with DS.
- B)** For preliminary evidence of safety, we will require no observation of serious or severe adverse effects possibly, probably, or definitely associated with fluoxetine.
- C)** For preliminary evidence of tolerability, we will require an observed drop-out rate due to adverse effects less than 36%.

Specific Aim 2: Collect preliminary data comparing the usefulness of existing depression rating scales in characterizing participants and assessing depression treatment effects.

A variety of outcome measures of depression will be used to better assess their applicability and feasibility in the DS population. The relative performance of the scales will be evaluated based on their sensitivity to change and their association with clinical improvement ratings. Percent of item-level missing data, and any feedback on the appropriateness or ease of use of the scales from participants, including their legal guardians, or study personnel, will also be taken into account.

Specific Aim 3: Estimate the mean therapeutic dose of fluoxetine for adults with DS for treating major depressive disorder (MDD).

We will report the average dose of fluoxetine at the end of 16 weeks of treatment.

We expect our results to: 1) provide preliminary evidence on the safety, effectiveness, and tolerability of fluoxetine for the treatment of MDD in DS; 2) assess the relative performance of existing depression rating scales in DS; and 3) provide information on fluoxetine dosing. Currently there is no prospective evidence on the safety, efficacy, and tolerability of any medication for the treatment of depression in DS. The lack of evidence-based guidelines for the treatment of depression in DS likely contributes to the decreased awareness of and under/misdiagnosis of this largely treatable condition. Adults with DS and comorbid depression may be mistakenly diagnosed with dementia, another neuropsychiatric condition for which there is much greater awareness in DS, but few effective treatments.

Data from this study will lay the foundation for the development of evidence-based guidelines for the treatment of depression in DS which will help increase awareness of this comorbidity and promote systematic screening and treatment. Medication treatment strategies for depression used in the general population likely need to be adapted to be safe, tolerable, and effective for adults with DS. Our clinical experience and pilot data suggest that adults with DS may respond to much lower dosages of fluoxetine than are used in the general population and that higher dosages may be associated with intolerable behavioral side effects such as anxiety or behavioral activation [20]. Data from this proposed study will inform best practices for dosing antidepressants in adults with DS. Finally, no specific depression rating

scales have been developed for or validated in DS. Data from this proposed study will inform which existing rating scales can detect depression in DS and which are sensitive to change with treatment. All the rating scales used in this study are in the public domain and therefore can easily be used in clinical practice. The identification of an appropriate rating scale will allow non-psychiatric specialists such as primary care providers as well as psychiatrists with less experience treating adults with developmental disabilities to screen for depression and monitor treatment effects. Overall, the data from this study is expected to improve the accessibility and quality of treatment for depression in DS, a common comorbidity which affects up to 70% of adults with this syndrome

3. General Description of Study Design

[figure not shown]
We are proposing a 16-week, prospective flexibly-dosed, open-label trial of fluoxetine for the treatment of major depressive disorder (MDD) in adults with DS. Participants will be seen at screen, baseline, and following 4, 8, 12, and 16 weeks of treatment. The duration of the trial will allow us to adjust the dose of fluoxetine over the first 12 weeks and allow for stable dosing during the final 4 weeks of the trial. We may complete visits remotely utilizing secure videoconferencing platforms such as Zoom or by phone, as necessary.

*Accommodations for Out of state patients and virtual visits**

The same IRB-approved accommodations for out of state patients our group is using in a similar open-label drug trial of buspirone for anxiety in Williams syndrome (Protocol #2021P000376) will be utilized for this study. All participants will be seen for either an in-person or virtual visit for the screen and baseline visits, the primary purpose of which are to establish care and determine the diagnosis and treatment plan. The prescription of fluoxetine will occur at the time of the baseline visit. In accordance with the Mass General Brigham Virtual Visit Procedures (applicable as of April 1, 2021), virtual visits will only be conducted with patients who are located in New England and Florida at the time of the visit and only by attending physicians who are licensed in those states. In accordance with the "FAQs for Mass General Brigham Clinicians: Changes to Procedures for Out of State Virtual Visits" (July 15, 2021) guidelines, the weeks 2, 4, 6, 8, 10, 12, and 16 visits will be conducted as "Customary telephone calls." These visits will consist of brief, logistical conversations with the purpose of communicating with subjects, adjusting prescriptions, and ensuring continuity of care by reviewing adverse effects and concomitant treatments/medications. If at any time during a "Customary telephone call" the study team learns of information concerning for new symptoms that are inconsistent with the diagnosis established during the baseline visit, symptoms that warrant a different treatment plan, or any other reason that in the attending physician's judgment that warrants a medical visit, the subject will be referred for either local clinical care within their state or offered an in-person visit in Massachusetts.

**In person regular and endpoint visits will be offered for all participants who are able to attend and participate in study procedures.*

Study staff will provide participants with information on how to access the video conferencing platform. Study staff will launch the video conferencing in a private and secure area and ask participants to refrain from taking screenshots, photographs, or recordings of any kind with any electronic equipment. Study staff will remind participants that video/phone meetings are similar to a home visit and that we may learn more about their home and/or the people living with them than during a visit at the hospital. For example, study staff may learn information that must be reported to public health or public safety authorities. The Informed consent describes the legal obligation to report known or suspected child or elder abuse. If study staff make such a report, the public health and safety authorities can use the information as they see fit and may end up sharing it with other government agencies.

4. Subject Selection

Twenty-five adults (18-45 years of age), with a diagnosis of DS exhibiting clinically significant symptoms of MDD on standardized rating scales will be included in this trial. Subjects will be selected to participate in the study based on the following Eligibility Criteria:

Inclusion Criteria

1. **Age 18-45 years.**
2. **Diagnosis of DS** confirmed via genetic testing or a clinical diagnosis made by a clinician with significant experience treating patients with DS.
3. **Diagnosis of major depressive disorder** based on Diagnostic and Statistical Manual of Mental Disorders, Fifth Edition (DSM-5) criteria, confirmed through the Structured Clinical Interview for DSM-5 (SCID-5).
4. **Moderately severe depression as evidenced by a Montgomery-Asberg Depression Rating Scale (MADRS) score of 20 or greater** at Screen and Baseline. A severity score on the MADRS was chosen as an inclusion criterion since it has been demonstrated to be sensitive to change in adults with MDD [27].
5. **A Clinical Global Impression Severity Item score ≥ 4 (moderate)** for depression symptoms at Screen and Baseline.

Exclusion Criteria

1. **Active primary diagnosis of obsessive-compulsive disorder, posttraumatic stress disorder, bipolar disorder, psychosis, or substance use disorder.** These disorders are exclusionary since the primary treatment of these disorders may require acute psychosocial or medication treatments that would confound the assessments used in this study. We will evaluate for these disorders using the corresponding SCID-5 modules.
2. **Current or previous diagnosis of dementia, or use of medication to treat dementia.** Given the potential overlap between depression and dementia symptoms, we want to ensure we are administering fluoxetine to patients with a diagnosis of depression.

3. **Presence of any past or present conditions that would make treatment with fluoxetine unsafe.** This includes allergy to fluoxetine, liver or kidney disease, unstable heart disease, and/or pregnancy (or being sexually active without using acceptable methods to prevent pregnancy).
4. **Use of selective serotonin reuptake inhibitors (SSRIs), serotonin norepinephrine reuptake inhibitors (SNRIs), tricyclic antidepressants (TCAs), monoamine oxidase inhibitors (MAOIs), bupropion, mirtazapine, antipsychotics, lithium, valproic acid, or carbamazepine.** Subjects will need to be off these classes of medications for at least 5 elimination half-lives prior to beginning the trial.
5. **Use of other psychotropic medications which are ineffective, poorly tolerated, or sub-optimal in terms of dose.** A board-certified psychiatrist will assess any other psychotropic medications being used and determine whether they are effective, tolerated, and optimal in terms of dose. If medications are ineffective, poorly tolerated, or sub-optimal in terms of dose, the study psychiatrist will work with the subject and his/her treatment team to either taper or optimize the dose of psychotropic medications prior to study enrollment. Concurrent use of a psychotropic medication (other than SSRIs, SNRIs, TCAs, MAOIs, bupropion, mirtazapine, antipsychotics, lithium, valproic acid, or carbamazepine) will be allowed if the dose has been stable for 30 days and if they meet the criteria of effectiveness, tolerability, and dose.
6. **Previous adequate trial of fluoxetine.** An adequate trial will be defined as a total daily dose of ≥ 30 mg for at least 4 weeks. In addition, subjects who developed significant adverse effects during a trial of fluoxetine at any dose or duration will be excluded.
7. **Severe or profound intellectual disability based on clinical assessment and review of standardized assessment of cognitive skills.** Participants determined to have severe or profound intellectual disability will be excluded.
8. **Use of medications that pose a clinically significant risk of a drug-drug interaction with fluoxetine.**

Participants will be recruited from several different sources. We will advertise this study in the community (primary and subspecialty pediatric and adult clinics such as the Lurie Center) and via the National Down Syndrome Society. In addition, [name] (Co-Investigator) is the Chief of the MGH Down Syndrome Psychiatry Clinic and is the primary psychiatrist for the MGH Down Syndrome Program. She receives more than 30 referrals for new DS psychiatric consultations each year. Given the size of the Massachusetts General Hospital Down Syndrome Program, we anticipate local advertisements, flyers, recruitment letters and social media posts will supplement our recruitment efforts. Subjects will be recruited using an advertisement in MGB's Rally platform. Subjects will also be recruited from the clinic's recruitment database (Lurie Center Research Recruitment) that has been approved by the IRB (2023P000099). The approved study research invitation letter will also be sent via patient gateway to Mass General Brigham patients diagnosed with Down syndrome and meeting age criteria utilizing a queried list from the Mass General Brigham Research Patient Data Registry (RPDR) (2013P000347). All advertisements will be pre-approved by the Institutional Review Board.

All genders and racial groups will be recruited as they are represented in the population of study. Minority group members will be recruited in approximate proportion to their representation in the regions represented. We are committed to ensuring that the minority representation of this study population is characteristic of the regions involved and that the findings are thus generalizable.

5. Subject Enrollment

Informed Consent and Assent Procedures

Subjects and their legal guardians who are interested in participating in the study will have a face-to-face interview with the PI, co-I, and/or the research coordinator/assistant where the nature of the project, the risks, the benefits, and the alternatives to participation in the project are discussed. Prior to engaging in research, formal written consent will be obtained from the parent(s)/legal guardian(s) on an IRB-approved consent form. The signed consent form will be scanned into EPIC. Based upon parent report and/or clinical observation, if the subject is able to comprehend the consent document and understands the risks

and benefits involved in the study, verbal or written assent will be obtained, and an IRB-approved form will be used for this purpose. The only exception will be for subjects with lower developmental levels who are assessed as incapable of participating in even a simplified discussion of benefits, risks, and alternatives. The PI or other physician co-investigator will sign a consent/assent checklist. The signature indicates the physician's assessment of the subject's capacity to provide assent, and if so, the type of assent (verbal or written). How capacity to assent was determined will also be documented. The determination of capacity to assent includes a clinical assent evaluation performed by a physician. The evaluation includes assessing the subject's ability to remain present and attentive to the discussion of study procedures, ability to understand study procedures, ability to communicate a choice clearly and consistently as to whether to participate, the subject's understanding of the risks/benefits/alternatives to study participation, and feedback from the subject's LAR. If the physician determines the subject does have the capacity to assent, then the type of assent is determined based on verbal and written abilities observed in the consent/assent discussion and information on the subject's abilities gathered from the LAR. All attempts to obtain assent and/or observation regarding the subject's ability to provide assent will be thoroughly documented. To minimize coercion, an investigator who is also the treating physician of a potential subject will **not** be present during the consent process.

We anticipate that some adults with DS may not be able to fully participate in all study visits for a variety of reasons, including cognitive/communicative limitations and lack of cooperation resulting in inability to fully complete all depression assessments and questionnaires. Lack of cooperation during study visits due to emotional dysregulation such as repeated requests for a break, and verbalizations of distress will not be considered withdrawal of assent. However, the study physician would evaluate the subject on a case-by-case basis to determine if more sustained and significant behaviors, such as refusal to take the study medication and/or refusal to participate in even brief evaluations with the study physician during visits, would constitute withdrawal of assent.

Non-English speaking individuals will not be enrolled in this study as most of the outcome measures are validated and normed for the English language only.

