A meta-analysis investigating the effectiveness of fluoxetine treatment estimated the intent-to-treat probability of response to treatment as measured using the CGI-I to be 44% [32]. In addition, the lower bound of the 95% confidence interval for response to treatment from our retrospective study excluded values less than or equal to 50%. A sample size of 20 provides a greater than 90% chance of observing a response rate of 35% or greater if the population probability of response is 44% or greater and a greater than 90% chance of observing a response rate less than 35% if the true probability of response is 20% or less. For safety outcomes, if there is a serious or severe adverse event associated with fluoxetine treatment in the population of adults with DS that occurs with a frequency of 10% or greater, we will have an 85% or greater chance of observing it in the study and concluding there are safety concerns with fluoxetine use for depression in adults with DS, assuming at least 90% (n=18) of participants remain in the study long enough to experience the event. For tolerability, assuming at least 85% of patients complete treatment or withdraw due to adverse effects, a sample size of 20 provides greater than 90% chance of observing a dropout rate due to side effects less than 36%, assuming at least 80% of adults with DS and depression in the population can tolerate a 16 week treatment course, and at least an 80% chance of observing a dropout rate due to side effects of 36% or greater assuming no more than 50% of adults with DS can tolerate a 16 week treatment course. Assuming an overall completion rate of 70%, a sample size of 20 also allows estimation of mean changes in depression scale score and mean dosage at study completion with a 95% confidence interval half width of 0.6 standard deviations, assuming a correlation of 0.5 between baseline and week 16 measurements.

Statistical Analysis Plan:

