We will estimate percentage response to fluoxetine treatment, and corresponding 95% confidence interval, for adults with DS using the proportion of participants with CGI-I scores ≤ 2 at 16 weeks. Participants with missing 16-week CGI-I scores will be treated as non-responders. Frequency of all side effects and adverse events and corresponding 95% confidence intervals will be tabulated. Percent tolerating treatment and corresponding 95% confidence intervals will be estimated using the proportion of participants who did not withdraw from the study before 16 weeks due to reasons other than side effects or an adverse event who discontinue treatment due to side effects or an adverse event. We will also use the 16-week study retention rate and corresponding 95% confidence interval, calculated as the proportion of the participants enrolling in the study who remain in the study for 16 weeks, as a measure of feasibility.

To estimate changes in depression scale scores, including the MADRS, HAM-D, GDS-LD, and GDS-CS, we will use repeated measures linear regression models, as implemented in PROC MIXED in SAS and fit using REML estimation, with repeated measurements of clinical scores as outcomes and time, in categories, as the predictor. We will allow unstructured covariance between repeated measurements from the same participant. Our primary interest will be only in the difference between baseline and week 16 scores, but all observed scores will be included as outcomes, given that partially observed scores may be informative for estimation. We will obtain an estimate of 16-week change and corresponding 95% confidence interval using a contrast of the week 16 and baseline model parameters. Sensitivity to change will be compared between scales using standardized effect sizes, calculated using the model-estimated 16-week change in each outcome divided by 1) the model-estimated standard deviation of the outcome at baseline and 2) the model-estimated standard deviation of the change score. Spearman correlations will quantify the strength of association between change in depression scale score and CGI-I ratings among those with observed 16-week data. We will also tabulate and compare the percent of item-level missing data for each scale.

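### Section 4 plans 25 participants and Section 9 is calculated for 20; at either size the chance of meeting the 35% response rule at a true 44% is about 85%, not above 90%

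*Combined protocol and SAP*

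**What the plan says.** Section 4 (Subject Selection) sets the number to be included: "Twenty-five adults (18-45 years of age), with a diagnosis of DS".

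Section 9 (Sample Size Considerations) works from a different number: "A sample size of 20 provides a greater than 90% chance of observing a response rate of 35% or greater". The condition attached is a true response probability of at least 44%, a figure taken from a meta-analysis of fluoxetine. The same sentence claims a better than 90% chance of falling below 35% when the true probability is at most 20%.

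Section 9 then applies losses to the 20. For safety it works "assuming at least 90% (n=18) of participants remain in the study long enough to experience the event". For precision it writes "Assuming an overall completion rate of 70%, a sample size of 20 also allows estimation of mean changes". For tolerability it assumes that 85% either complete or withdraw because of adverse effects.

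Section 2 (Specific Aim 1) sets the effectiveness criterion as a percentage, not a count: "For preliminary evidence of effectiveness, we will require an observed response rate" of at least 35%, response being a CGI-I rating of 1 or 2 at week 16. The Statistical Analysis Plan in Section 9 adds: "Participants with missing 16-week CGI-I scores will be treated as non-responders".

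**The concern.** There are two separate faults.

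1. **Two sample sizes with no bridge.** No section gives an over-enrolment, dropout or screen-failure allowance leading from 20 to 25. Although 20/0.80 = 25, no 20% inflation is stated. Such an inflation would also fit poorly: Section 9 already removes losses from the 20, and a missing primary outcome counts as non-response, so dropouts stay in the denominator.
2. **A probability that looks too high.** With so few participants, a cut-off of 35% lies only 9 percentage points below the assumed 44%, and a better than 90% chance of clearing it looked doubtful.

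The CGI-I response rate is the primary outcome, and the 35% rule is the trial's test of preliminary effectiveness ahead of a placebo-controlled trial. Someone interpreting a negative result would rely on the stated chance of passing. If that figure is too favourable, a miss will be read as stronger evidence against the drug than it is.

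**Working it through.** **Inputs.** N = 20 (Section 9) or 25 (Section 4); pass if the observed rate is at least 35% (Section 2); true response 44% or 20% (Section 9); missing CGI-I counted as non-response (Section 9). X is the number of responders, binomial(N, p).

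**Step 1: which number is the 20?** The safety calculation equates 90% with 18, and 0.90 × 20 = 18. The tolerability and precision figures reproduce from 0.85 × 20 = 17 and 0.70 × 20 = 14 (step 4). So 20 is the number before losses.

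**Step 2: responders needed.** The count is 0.35 × N rounded up.
- N = 20: 7.0, so 7 (35%).
- N = 25: 8.75, so 9 (36%).

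Eight responders pass at 20 (8/20 = 40%) and fail at 25 (8/25 = 32%).

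**Step 3: the stated chance of passing at 44%.**
- P(X ≥ 7 | 20, 0.44) = 0.8501
- P(X ≥ 9 | 25, 0.44) = 0.8431

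The stated figure of more than 90% is not reproduced at either size. Other routes were tried:
- The normal approximation gives 79.1% at 20 (85.0% with continuity correction) and 81.8% at 25 (86.6%).
- For every N from 17 to 25, the largest exact value is 85.0%.
- A cut-off one responder lower exceeds 90% (6/20: 93.4%; 8/25: 92.3%). But those rates are 30% and 32%, which fail the 35% rule, and the chance of a negative result at 20% response would drop to 80.4% and 89.1%, below the claimed 90%.

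The response rate at which the chance reaches 90% is 46.7% at both sizes; at 47% the chance is 90.4% (N = 20) and 90.5% (N = 25). Holding 44% and the 35% rule, the smallest N that exceeds 90% is 40 (at least 14 responders, 90.5%).

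**Step 4: the other Section 9 figures.**

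| Quantity | Stated | N = 20 | N = 25 |
|---|---|---|---|
| Below 35% when true response is 20% | >90% | P(X ≤ 6) = 91.3% | P(X ≤ 8) = 95.3% |
| Detecting a 10% event | ≥85% | 1 − 0.9^18 = 85.0% | 1 − 0.9^22 = 90.2% |
| Dropout below 36% when true dropout is 20% | >90% | 17 evaluable, ≤6: 96.2% | 21 evaluable, ≤7: 95.7% |
| Dropout 36% or more when true dropout is 50% | ≥80% | 17 evaluable, ≥7: 83.4% | 21 evaluable, ≥8: 90.5% |
| 95% CI half-width for mean change | 0.6 SD | 14 completers: 0.58 SD | 17–18 completers: 0.51–0.50 SD |

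For N = 25 the retention fractions give 22.5, 21.25 and 17.5, taken as 22, 21 and 17 to 18. For the half-width, a correlation of 0.5 makes the SD of change √(2 × (1 − 0.5)) = 1 score SD, so the half-width is t/√n: 2.160/√14 = 0.58.

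All of these agree with the plan at 20 and meet or better the stated level at 25. Only the favourable-response claim fails.

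**The case against.** A percentage rule scales with whatever number is enrolled. Anyone applying Section 2 and the analysis plan to the final data could say whether 35% was reached, so the decision itself is not ambiguous. That stands: what the mismatch leaves open is the planned count, not the rule. It follows that a fixed count should not replace the percentage, since 22 participants would need 8 responders and 23 would need 9.

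The 20-versus-25 difference also changes little. The chance of passing at 44% moves by 0.7 points (85.0% to 84.3%), and no other figure falls below its stated level. That stands too; this half of the point is a reconciliation, and the real error is the probability in Section 9.

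The trial is single-arm and preliminary with no hypothesis test, and its protection against a false positive is correctly stated. Section 9 also cites retrospective data whose lower confidence bound lies above 50%; at a true 50% the chance of passing is 94.2% (N = 20) or 94.6% (N = 25). This limits the practical damage but does not make the sentence true: its condition is 44% or more, so it has to hold at 44%.

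Finally, the analysis plan says only participants for the response denominator, so reading it as all enrolled is an inference from the non-responder rule. The inference is reasonable, but it should be written down, with screen failures addressed.

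**Conclusion.** The concern holds. Sections 4 and 9 give different sample sizes with no stated link. The claimed better than 90% chance of meeting the effectiveness criterion at 44% response is wrong at both: 85.0% at 20 and 84.3% at 25, at least 5 points short. The risk of missing the criterion when the plan's own assumption is true is 15.0% or 15.7%, about one in six or seven.

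This rests on independent participants with a common response probability, all of them in the denominator, and 44% as the probability of response after missing ratings are counted as failures. The last matches the intent-to-treat basis that Section 9 gives for the 44%. The error is confined to that one operating characteristic; the remaining planning figures are sound, and the size mismatch has little effect on them.

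**What to change.** - State one enrolled number in Sections 4 and 9. If 25 includes an allowance over 20, say what it is for.
- Replace the better than 90% claim at 44% response with about 85% (N = 20) or about 84% (N = 25). Alternatively, keep 90% and state that it holds from about 47% response.
- Beside the 35% rule, show the count it implies at the planned number (7 of 20 or 9 of 25). Make clear that the percentage governs if actual enrolment differs.
- Define the response denominator explicitly as all enrolled participants, and say whether people who consent but fail screening count as enrolled.
- If 25 is kept, update the rest of Section 9: 95.3% for a negative result at 20% response, 90.2% for safety detection, 95.7% and 90.5% for tolerability, and a half-width of about 0.5 SD.

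The cost is rewording and a short recalculation. No patients are added and the criterion does not change. The only loss is a less favourable stated chance of success at 44%.
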